Images were reconstructed using iterative reconstruction algorithm (strength level 3/5, Admire, Siemens Healthineers) with 0.6 mm slice thickness at 350ms for non-contrast images and 220-440ms (20ms intervals) for CCTA images. All studies were blinded as to the nitroglycerin delivery method. Coronary calcium scores (Agatston method) and severity of any coronary artery disease were assessed from the radiology reports.

Quantitative Analysis

A cardiovascular imaging-trained radiologist with six years of experience (X.X.)(anonymized) measured coronary diameters at seven locations (**Figure 2**) using a 3D-workstation (Aquarius v.4.4.12, Terarecon Inc., Foster City, CA). These locations were predetermined as: (1) proximal right coronary artery (RCA) 1.5 cm distal from the ostium; (2) mid RCA 1.0 cm proximal of the acute marginal branch; (3) distal RCA 1.0 cm

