proximal of the bifurcation into posterior descending artery and right postero-lateral branch; (4) middle of the left main (LM); (5) proximal left anterior descending artery (LAD) 1.0 cm after LM bifurcation or, if less distance to the 1st diagonal branch, in the middle of the proximal LAD; (6) mid LAD 2.0 cm distal of 1st diagonal branch or if less distance to the 2nd diagonal branch, in the middle of mid LAD; and (7) left circumflex coronary artery 2.0 cm distal of the LM bifurcation. Positions were located in the non-contrast images and reaffirmed on CCTA images using a corresponding phase of the cardiac cycle. Locations with non-calcified or calcified plagues or unclear depiction of the coronary artery due to adjacent structures such as veins were avoided, and in those segments, the location of measurement was moved distally up to 1.0 cm from the original position while staying in the same coronary segment and avoiding bifurcations. If coronary diameters could not be measured at any of these positions, the location was excluded. We excluded stented or bypassed locations from measurements. All coronary diameters were measured twice at each location using short-axis views in an enlarged field-of-view and averaged using window width and level of 350 HU and 50 HU for non-contrast and 800 HU and 200 HU for CCTA images (Figure 2). Window settings were set based on preliminary measurements in 20 patients who underwent CCTA without nitroglycerin and therefore no diameter differences in non-contrast and CCTA images. Locations #1, #4, and #5 were defined as proximal-, locations #2 #6, and #7 as mid-, and location #3 as distal coronary segments.

Safety

By query, side effects were evaluated, including headache, dizziness, and nausea during the exam. The severity of headache was quantified on a 10-point scale ranging from 1 minimal- to 10 maximal-intensity.

Statistical Analysis

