Demographic and scan parameter summaries were calculated for the entire subject cohort and by nitroglycerin administration method. Categorical variables were summarized using frequencies and percentages, while continuous variables were summarized as means and standard deviations, or as median and interquartile range (25^{th} and 75^{th} percentiles) if the distribution of the variables were skewed. Differences in continuous variables by treatment were assessed using the Kruskal-Wallis test, and differences in categorical variables were assessed using either the Pearson χ^2 test, or Fisher's exact test. Changes of vital parameters pre- and posttreatment were compared using paired t-test.

A linear quantile (median) mixed-effects model was constructed to quantify the unadjusted association between treatment and vasodilation (contrast diameter/non-contrast diameter x 100) while accounting for dependencies within the data set due to multiple observations per subject. This modeling approach permitted the estimation of the median vasodilation as a function of covariates while avoiding the parametric modeling assumptions that are typically associated with linear mixed models. Estimates of fixed-effects, and their 95% Wald-type confidence intervals, were computed for all model

parameters. Linear combinations of these parameters were used to estimate overall effects, and effects by treatment.

Two additional models were constructed where we hierarchically accounted for patient demographics (i.e., age, gender, BMI and height) and then by patient demographics and disease severity measure (i.e., CA score). A subgroup analysis was performed where model parameters were estimated by proximal, mid and distal regions. Due to the explorative nature of this subgroup analysis, p-values were not adjusted for multiple comparisons.

All analyses were performed using R 3.4.3 (R-Core Team, 2017, Vienna, Austria) (20) and the lqmm R library (21).

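### The regional analysis measures distal dilation at one RCA site only, so any comparison with the distal region cannot separate region from vessel

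*Combined protocol and SAP*

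**What the plan says.** The Quantitative Analysis section of the combined protocol and SAP lists seven measurement sites.

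- Three are in the RCA: "1) proximal right coronary artery (RCA) 1.5 cm distal from the ostium" for site #1, and "2) mid RCA 1.0 cm proximal of the acute marginal branch; (3) distal RCA 1.0 cm" for sites #2 and #3, the last placed just before the vessel's terminal bifurcation.
- Four are in the left system: the left main (#4), two LAD sites (#5 and #6), and "7) left circumflex coronary artery 2.0 cm distal of the LM bifurcation" for site #7.

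The sites are then grouped: "Locations #1, #4, and #5 were defined as proximal-, locations #2 #6, and #7 as mid-, and location #3 as distal coronary segments".

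Statistical Analysis uses this grouping: "A subgroup analysis was performed where model parameters were estimated by proximal, mid and distal regions". That section calls the subgroup analysis exploratory and leaves its p-values unadjusted. The covariates named for the adjusted models are four demographic variables and then a CA score. Vessel is not among them, no comparison of regions within a vessel is planned, and no formal test between regions is stated.

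**The concern.** The region labelled distal coronary segments is a single RCA site, and no distal site in the left system is measured. A distal estimate set beside a proximal or mid estimate therefore compares an all-RCA group with groups that are mostly left coronary. Any RCA-versus-left difference, whether from physiology or from measurement, would be mixed into that comparison.

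Two kinds of conclusion are exposed. One is that distal coronary segments dilate more or less than proximal ones. The other is that one delivery method does relatively better distally. Either could be a property of the RCA, and the planned model could not show which. A formal treatment-by-region test on the same grouping would have the same problem.

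**Working it through.** The plan gives no figure for the regional analysis, so there is none to reproduce. Its sample size (66 per arm) does not bear on the point. The site list and grouping come from Quantitative Analysis. Values of v and g below are assumptions, in points of the vasodilation percentage.

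**1. Composition of each region**

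| Region | Sites | RCA | Left | RCA share |
|---|---|---|---|---|
| Proximal | #1, #4, #5 | 1 | 2 | 1/3 |
| Mid | #2, #6, #7 | 1 | 2 | 1/3 |
| Distal | #3 | 1 | 0 | 1 |

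**2. A vessel difference v with no regional gradient.** Let left sites have mean m and RCA sites m + v.

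- Proximal mean = m + v/3; mid mean = m + v/3; distal mean = m + v.
- Distal minus proximal = distal minus mid = v − v/3 = 2v/3.
- Mid minus proximal = 0. The RCA/left split is balanced there, although the left vessels differ (left main and LAD against LAD and circumflex).

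The factor 2/3 assumes that every site is measured. Unmeasurable, stented and bypassed locations are dropped, so the realised factor is 1 − p, where p is the RCA share among the measured proximal (or mid) observations. For illustration, p = 1/4 gives 0.75v and p = 1/2 gives 0.50v.

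**3. Medians instead of means.** The plan models medians, so the result was checked by simulation. It used 66 patients per arm, 400 repeats, all sites measured, an assumed between-patient SD of 6 and residual SD of 8 points, and simple regional medians rather than the mixed-effects fit.

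| Assumed v | 2v/3 | Simulated distal minus proximal (medians) |
|---|---|---|
| 2 | 1.3 | 1.2 |
| 3 | 2.0 | 2.0 |
| 5 | 3.3 | 3.4 |
| 10 | 6.7 | 6.8 |

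**4. Comparisons of delivery methods**

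- Vessel main effect only: the arms share the same planned sites within a region, so v cancels (v/3 − v/3 = 0 in proximal and mid; v − v = 0 in distal). Simulated arm differences were at most 0.2 points in absolute value in every region.
- Treatment-by-vessel interaction g (an extra arm difference at RCA sites only) with no regional effect: the arm difference is g/3 proximal, g/3 mid and g distal. For g = 3 that is 1.0, 1.0 and 3.0; the simulated medians gave 0.9, 1.0 and 3.0. This pattern is what a treatment-by-region effect would look like.

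**5. What the collected sites can separate**

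- Region alone needs 3 parameters. Adding vessel (RCA or left) makes 4, and the seven-site design has rank 4. The additive model is therefore estimable: proximal and mid each contain both vessels and supply v.
- Region by vessel needs 6 parameters, but the design has rank 5 because the distal-left cell is empty. Whether the distal step differs between RCA and left cannot be estimated.
- If regions are fitted separately, vessel is constant in the distal fit and cannot be included there.
- Sites #1, #2 and #3 alone give proximal, mid and distal within one vessel, with no additivity assumption.

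**The case against.** The strongest reply is that the analysis is exploratory, that the plan states no distal-versus-proximal contrast, and that the trial's question is about randomised delivery methods. Within a region all arms use the same predetermined sites, so a vessel main effect does not bias the arm comparison. The primary model pools over sites and does not use the region labels. The grouping is stated openly, and site #3 is already named as distal RCA in the site list.

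Most of this stands, and it limits the point to interpretation across regions. It does not remove the point. The exploratory label is used to justify unadjusted p-values and does not settle what the distal estimate represents. Parallel estimates for three regions invite comparison even without a test, and randomisation does not separate treatment-by-vessel from treatment-by-region.

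A reader might go further and infer any of the following, none of which the documents support:

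- **A vessel difference will be reported as a distal effect.** The documents give no vessel-specific vasodilation, so the statement can only be conditional.
- **The delivery-method results within the distal region are biased.** That does not follow from a vessel main effect. An interaction would leave the arm difference valid for the distal RCA but mislabelled as distal in general.
- **A spurious regional difference of 3 points would matter because it equals the 3% equivalence range.** The Methods section sets that range for comparing delivery methods, not coronary regions.
- **The collected data can fully separate vessel from region.** They can do so only under additivity, because no distal left site exists.

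**Conclusion.** The point holds as a limit on what the exploratory regional analysis can conclude. The distal estimate is a distal RCA estimate. With all sites measured, two-thirds of any RCA-versus-left difference would enter a comparison of distal with proximal or mid, and more patients would not shrink it. The fraction is exact for means, approximate for medians, and shifts with site exclusions. Its size in points is unknown because the documents give no value for v. For delivery methods, the ambiguity arises only if treatment acts differently by vessel, which the documents neither show nor exclude. The pooled primary analysis is unaffected. This is an inexpensive improvement to a secondary analysis and does not threaten the trial's main result.

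**What to change.** 1. Report site #3 as distal RCA throughout, and do not generalise it to distal coronary segments.
2. Make comparisons across regions within the RCA, using #1, #2 and #3 as proximal, mid and distal of one vessel, with the patient-level dependence modelled as already planned. For delivery-method questions, examine treatment by site within these three.
3. Optionally, as support, fit all seven sites in one model with region and vessel (RCA or left) terms, adding their interactions with treatment where delivery method is the question. State that the distal term then rests on region and vessel effects being additive, because no distal left site is measured.

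The cost is a change of SAP wording and one re-specified exploratory model, with no new measurements. The RCA-only analysis uses 3 of 7 sites, so it is less precise and answers a question about the RCA only. The seven-site model recovers the other sites at the price of the additivity assumption. Neither shows how distal left segments behave. If the regional results have already been seen, the re-specified analysis should be labelled post hoc.

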Effects of Sublingual and Transdermal Administration of Nitroglycerin for Coronary CT Angiography on Image Quality

NCT#: NCT02961946

Study protocol and statistical analysis plan

October 14, 2018

Methods

This study had a prospective, randomized controlled design conducted at a single, academic hospital and was approved by our institution's review board, which required signed consent. The study was HIPAA compliant and registered at the Clinical Trials Registry (#NCT02961946) with the title "Effects of Sublingual and Transdermal Administration of Nitroglycerin for Coronary CT Angiography on Image Quality".

Based on prior literature, we hypothesized that mean coronary artery diameter before and after nitroglycerin application would be 2.86 mm and 3.26 mm, respectively, with 13.8% vasodilation (13). We assumed an equivalence range of 3% and determined a type-I error of (0.05/3=0.017) for a 3-group comparison with 80% power. In total, 198 individuals and 66 individuals per arm were necessary for a 3-group comparison.

Coronary artery vasodilation was the primary outcome. Secondary outcomes included changes in vital signs and frequency of side effects after nitroglycerin application. The dependent variable was the method of nitroglycerin delivery which could be lingual, sublingual, or transdermal.

Patient Selection

We identified potential subjects from our clinical cardiac CT schedule and included those whose study required an ECG-gated non-contrast CT followed by CCTA acquisitions. Subjects with a history of coronary revascularization were included. Exclusion criteria were age under 18 years, known hypersensitivity to nitroglycerin, closed-angle glaucoma, use of phosphodiesterase type 5 inhibitors within 72 hours prior to the study, conditions associated with elevated intracranial pressure, hemodynamic instability, critical aortic

stenosis, systolic blood pressure below 90 mmHg, pregnancy or lactating female, women with a positive urine pregnancy test, and subjects unwilling or unable to consent to participation.

Study Workflow

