The physician enrolling the subject to the study was blinded to the method of nitroglycerin administration. After obtaining informed consent, subjects were randomized (block randomization, block size=198) to one of three nitroglycerin delivery methods: (1) sublingual as a tablet (2x0.4 mg, Nitrostat, Pfizer Inc., NY), (2) lingual as a spray (2x0.4 mg, Nitrolingual, Pohl-Boskamp, Hohenlockstedt, Germany), or (3) transdermal as a patch (2x0.4 mg/h, Nitro-Dur, Merck&Co Inc., NJ). After assessing initial vital signs (heart rate, rhythm, and blood pressure), non-contrast CT was acquired. Subsequently, nitroglycerin was administered. Patches were placed on the upper chest, taking care to avoid body hair. The transdermal delivery method required an application time of at least 45 minutes, while lingual and sublingual nitroglycerin required 5 minutes application time before CCTA acquisition (Figure 1). After CCTA, the patches were removed, and the location was inspected for skin reaction, while spray and tablets did not require further interaction. Next, we remeasured vital signs and asked for symptoms of allergic-type reactions and if sublingual tablets had completely dissolved. Systolic blood pressure >180 mmHg or a drop of >10 mmHg compared to initial values required observation and followup until normalization. Finally, patients filled out a guery asking about side effects during the exam.

Image Acquisition

All individuals were scanned on a 128-slice dual-source CT (Somatom Definition Flash, Siemens Healthineers, Forchheim, Germany). Scan length was from carina to diaphragm and was extended if necessary. Scan parameters were as follows: non-contrast CT (prospectively-ECG-triggered at 350ms after the R wave, fixed 120kV, mA adjusted to body size, with a reference of 80 mAs [CareDose4D, Siemens Healthineers], 64x0.6mm collimation), CCTA (prospectively-ECG-triggered for heart rates <85 bpm, ≥85 bpm retrospectively-ECG-gated, with an acquisition window in late systole to early diastole (220-400 msec after the R-wave), 80-120kV with optimal kV [CarekV, Siemens Healthineers] and automatic mA selection based on the scout scan, reference 280 mAs, 64x0.6mm collimation). No beta-blocker was administered, as per our standard site practice.

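### Side effects are asked about once, for the whole exam, with no query before application, and the time from application to query is at least 40 minutes longer for patch than for tablet or spray

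*Combined protocol and SAP*

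**What the plan says.** The Methods section defines the outcome by its relation to the drug: "Secondary outcomes included changes in vital signs and frequency of side effects after nitroglycerin application".

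The Safety section gives the measurement: "By query, side effects were evaluated, including headache, dizziness, and nausea during the exam". For headache there is also a score: "The severity of headache was quantified on a 10-point scale ranging from 1 minimal- to 10 maximal-intensity".

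Study Workflow gives the order of events. Before the drug: "After assessing initial vital signs (heart rate, rhythm, and blood pressure), non-contrast CT was acquired". Nitroglycerin follows, and then a wait that depends on the arm: "The transdermal delivery method required an application time of at least 45 minutes, while lingual and sublingual nitroglycerin required 5 minutes application time". After CCTA come patch removal and skin inspection (patch arm only), repeat vital signs, and questions on allergic-type symptoms and tablet dissolution. The side-effect form is the last step: "Finally, patients filled out a guery asking about side effects during the exam".

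Statistical Analysis does not name side effects. Its general rule for categorical variables by treatment is a Pearson chi-square or Fisher's exact test. No adjustment for observation time or for symptoms before application is stated.

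**The concern.** There are two separate gaps between the stated outcome and what is collected.

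1. **Start of the window.** The outcome concerns symptoms after the drug. The form concerns the exam, which by the workflow includes a non-contrast CT before the drug. No symptom assessment before application is described, so existing symptoms cannot be separated from new ones.
2. **Length of the window.** The query is tied to the end of the visit, not to a time after application. The time at risk of being counted is therefore set by the assigned arm, and randomisation cannot balance a quantity that the assignment itself determines.

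At stake is the between-arm comparison of tolerability. Read as a comparison of side-effect rates under equal observation, it would partly reflect how long each group was observed.

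**Working it through.** **Inputs from the documents.** Wait from application to CCTA: at least 45 minutes for patch, 5 minutes for tablet and spray (Study Workflow). Arm size: 198/3 = 66 (Methods). The plan gives no expected rate, power or sample size for side effects, so there is no figure of its own to reproduce here.

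**Assumptions, not in the documents.** Time *t* from the end of the wait to the query, taken as the same in every arm. Background symptom rate *r* per hour, constant and identical in every arm.

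**Step 1: length of the window.** Window = wait + *t*. The difference is (45 + t) − (5 + t) = 40 minutes for any *t*. It is a minimum because 45 is a minimum, and it takes the 5-minute wait as kept. The ratio (45 + t)/(5 + t) does depend on *t*:

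| t (min) | Patch (min) | Tablet/spray (min) | Ratio |
|---|---|---|---|
| 5 | 50 | 10 | 5.0 |
| 10 | 55 | 15 | 3.7 |
| 20 | 65 | 25 | 2.6 |
| 30 | 75 | 35 | 2.1 |

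**Step 2: background symptoms from window length alone.** p = 1 − exp(−r × window/60), with t = 10. For r = 0.10 and patch: 1 − exp(−0.10 × 55/60) = 8.8%.

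| r per hour | Tablet/spray | Patch | Gap (points) | Expected count per 66 |
|---|---|---|---|---|
| 2% | 0.5% | 1.8% | 1.3 | 0.3 vs 1.2 |
| 5% | 1.2% | 4.5% | 3.2 | 0.8 vs 3.0 |
| 10% | 2.5% | 8.8% | 6.3 | 1.6 vs 5.8 |

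**Step 3: chance of a significant pairwise result from Step 2 alone.** Exact probabilities come from summing over all pairs of binomial counts with 66 per arm, two-sided 0.05:

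| r per hour | Fisher's exact | Pearson chi-square, uncorrected |
|---|---|---|
| 2% | 0.1% | 2.3% |
| 5% | 3.6% | 16% |
| 10% | 19% | 34% |

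The answer depends heavily on the assumed rate and on which of the two listed tests is used.

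**Step 4: direction.** A longer patch window adds unrelated symptoms to the patch count. A shorter tablet and spray window drops symptoms that start after the query. The first raises one side of the comparison and the second lowers the other, so both widen the gap against the patch. The second cannot be sized from the documents.

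**Step 5: symptoms present on arrival.** Suppose a share *b* arrives with a symptom, all of these are counted, and new symptoms are independent of them. The observed proportion is then b + (1 − b)p. With an assumed b = 10% and the last row of Step 2:

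- patch: 0.10 + 0.90 × 0.0876 = 17.9%
- tablet/spray: 0.10 + 0.90 × 0.0247 = 12.2%
- gap: 5.7 points instead of 6.3
- standard error of the gap: √[(0.179 × 0.821 + 0.122 × 0.878)/66] = 6.2 points, against √[(0.088 × 0.912 + 0.025 × 0.975)/66] = 4.0 points without arrival symptoms

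Arrival symptoms thus raise both rates and blur the comparison. They do not create a difference between arms where none exists.

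**The case against.** The strongest defence is that the longer wait belongs to the patch. A patient given a patch does spend that time in the exam, and symptoms over each method's whole exam are a legitimate measure of how the workflows compare. The outcome is secondary and carries no power claim. This stands, and it determines how the comparison should be interpreted. It does not answer the missing query before application, and the plan does not say that a whole-exam comparison is what it intends.

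It is also fair that the magnitude rests on assumed rates, that at low rates a significant artefact is unlikely, and that Figure 1 is not available and might add timing detail.

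Several stronger readings are tempting but not supported:

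- **A ninefold window.** 45/5 compares only the waits. The scan and later steps are added in every arm, so the ratio is smaller and unknown. The 40-minute difference is what the text supports.
- **Arrival symptoms bias the arms.** Randomisation balances them in expectation (Step 5). Nor does the text show how they are counted, since the form's wording is not given.
- **Contrast symptoms distort the comparison.** CCTA is done in every arm, and the steps from scan to query are the same apart from patch removal.
- **Blood-pressure observation lengthens the window.** The form is listed last, but nothing says that it waits for normalisation or that the recall period covers such observation.
- **The two distortions offset each other.** Step 4 shows that they add. An opposing effect is possible, such as poorer recall of brief early symptoms over a longer exam, but the documents do not allow it to be sized.
- **A fixed common window, such as 60 minutes, is the clear remedy.** It would need cards or calls mainly for tablet and spray, so mode of collection and non-return would differ by arm. It would also make follow-up after contrast unequal, which is roughly equal now. That is a trade-off, not a plain improvement.

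**Conclusion.** The point holds in this form. The stated outcome is side effects after application. The measurement is one query about the exam, with no symptom assessment beforehand and no common time after application. From the documents alone, the period from application to query is at least 40 minutes longer for patch, taking the post-wait steps as equally long in all arms. Both named consequences of that gap count against the patch.

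Only the 40 minutes is firm. The 1.3 to 6.3 points of spurious difference rest on an assumed 10 minutes of later steps and on assumed background rates of 2% to 10% per hour. Missed late symptoms would come on top.

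This is a moderate issue in a secondary safety outcome. A reader might infer that the side-effect comparison is void or that the vasodilation result is in doubt. Neither follows: whole-exam tolerability can still be reported, and the primary outcome does not use the query.

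**What to change.** 1. Give the same short query (headache with its score, dizziness, nausea) before application, and define the outcome as new or worsened symptoms. This brings the measurement into line with the outcome in Methods and removes arrival symptoms from the rates.
2. Record the clock times of application and of the query, and report the window length by arm.
3. State in Statistical Analysis that the between-arm comparison describes tolerability over each method's whole exam and is not a comparison of side-effect rates at equal exposure.

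Item 1 does not equalise the windows; items 2 and 3 make the remaining difference visible and keep the conclusion within what the data support.

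The cost is one extra short form per patient and two recorded times, with no extra visit, scan or reader. The document is written in the past tense. If collection is complete, item 1 is no longer possible, but item 3 still is, and item 2 is where times were recorded. The report should then say that symptoms before application were not assessed.

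### Vital-sign change is a secondary outcome of a three-arm randomised trial, but no baseline-adjusted difference between arms with an interval is planned

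*Combined protocol and SAP*

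**What the plan says.** The outcome statement in Methods reads: "Secondary outcomes included changes in vital signs and frequency of side effects after nitroglycerin application". Under Study Workflow, "subjects were randomized (block randomization, block size=198) to one of three nitroglycerin delivery methods".

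Both readings needed for a change are taken. Before treatment: "After assessing initial vital signs (heart rate, rhythm, and blood pressure), non-contrast CT was acquired". After the contrast scan: "Next, we remeasured vital signs and asked for symptoms of allergic-type reactions".

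Statistical Analysis has two sentences that could bear on this outcome:

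- One names it: "Changes of vital parameters pre- and posttreatment were compared using paired t-test". It does not say whether the test is pooled over arms or run within each arm.
- One is general and comes shortly before: "Differences in continuous variables by treatment were assessed using the Kruskal-Wallis test". It mentions neither vital signs nor change scores.

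Effect estimates with intervals are planned only for the vasodilation model: "Estimates of fixed-effects, and their 95% Wald-type confidence intervals, were computed for all model" parameters. The covariates of its adjusted versions are age, gender, BMI, height and calcium score. No initial vital sign is among them.

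**The concern.** The randomised question for this outcome is how much more blood pressure or heart rate changes with one delivery method than with another, and how precisely that is known. A paired test asks only whether the mean changed over time. Its result mixes the drug effect with the effects of the scan and of elapsed time, and it makes no use of the randomisation. If Kruskal-Wallis is meant to apply to the changes, the trial gains a valid omnibus p-value but still no estimate of any arm difference. Readers comparing tablet, spray and patch on haemodynamic effect would have p-values and no effect sizes. If the paired tests are run by arm, readers may also take a significant result in one arm and a non-significant result in another as evidence of a difference.

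**Working it through.** The plan states no power or precision for vital signs, so there is no figure of its own to reproduce. The sample size of 66 per arm (198 in total) is set on vasodilation and is used here only as the number available.

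**Inputs.** From the documents: n = 66 per arm, three arms. Assumed, because the documents give nothing: pre/post correlation ρ of 0.5, 0.6 or 0.8, and equal pre and post SDs. Results are in units of that SD unless stated otherwise.

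**1. What each planned test can show.** Simulation with a systolic SD of 15 mmHg and ρ = 0.6 (both assumed), 5,000 trials per scenario:

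- The pooled paired t-test was significant in 100% of trials with true drops of 10, 10 and 10 mmHg, and in 100% with drops of 6, 6 and 12 mmHg. It cannot tell equal arms from unequal arms.
- With a 5 mmHg drop in every arm, Kruskal-Wallis on the changes rejected in 4.9% of trials and ANCOVA in 4.8%. Both hold their nominal level.

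**2. Precision of a pairwise arm difference.** Residual SD is √(2(1−ρ)) for the change score and √(1−ρ²) for ANCOVA. The variance ratio is (1−ρ²)/(2(1−ρ)) = (1+ρ)/2. The 95% half-width is t × residual SD × √(2/66), with t ≈ 1.972, so t × √(2/66) ≈ 0.343.

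| ρ | Variance ratio | Half-width, change score | Half-width, ANCOVA | Equivalent n per arm |
|---|---|---|---|---|
| 0.5 | 0.75 | 1.000 × 0.343 = 0.343 | 0.866 × 0.343 = 0.297 | 66/0.75 = 88 |
| 0.6 | 0.80 | 0.894 × 0.343 = 0.307 | 0.800 × 0.343 = 0.275 | 66/0.80 = 82.5 |
| 0.8 | 0.90 | 0.632 × 0.343 = 0.217 | 0.600 × 0.343 = 0.206 | 66/0.90 = 73.3 |

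In mmHg, with an assumed SD of 15 and ρ = 0.5, the half-width is about 5.1 for the change score and 4.4 for ANCOVA. With an SD of 20 it is about 6.8 and 5.9.

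**3. Against the plan's most favourable reading.** The change-score difference in step 2 is a reference, not a planned analysis. The direct comparison is with Kruskal-Wallis on the changes. With an assumed SD of 15 mmHg and true drops of 6, 6 and 12 mmHg, simulated power was:

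| ρ | Kruskal-Wallis on change | ANCOVA |
|---|---|---|
| 0.5 | 63% | 78% |
| 0.6 | 72% | 84% |
| 0.8 | 96% | 98% |

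**4. Only if paired tests are run by arm and their p-values compared.** The text does not say this would be done. Let p be the power of one arm's paired t-test (noncentral t, 65 df, two-sided 0.05). Three arms with the same true change then disagree on significance with probability 1 − p³ − (1−p)³.

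| True change, in SDs of change | p | Probability of disagreement |
|---|---|---|
| 0 | 0.050 | 0.14 |
| 0.1 | 0.126 | 0.33 |
| 0.2 | 0.360 | 0.69 |
| 0.25 | 0.516 | 0.75 |
| 0.3 | 0.670 | 0.66 |
| 0.35 | 0.800 | 0.48 |
| 0.4 | 0.893 | 0.29 |
| 0.5 | 0.979 | 0.06 |

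**The case against.** The strongest reply is that a between-arm test is probably already planned. The general sentence on tests by treatment covers continuous and categorical variables, and no other sentence supplies a test for side effects, the companion secondary outcome. It is therefore natural to read it as serving both. On that reading a valid test with nominal error exists, and baseline adjustment is a matter of efficiency: the half-width shrinks by 0.046, 0.032 and 0.011 SD at ρ = 0.5, 0.6 and 0.8, and by only 0.004 SD at ρ = 0.9. The outcome is secondary, and the disagreement probabilities describe a procedure that the documents do not set out.

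Much of this stands. It would be wrong to say that no between-arm test could apply, the primary conclusion is untouched, and the disagreement figures should carry little weight. What the reply does not supply is an estimate: under its own reading there is still no arm difference and no interval. Nor is the efficiency gain an artefact of choosing a change-score comparator, since ANCOVA also had higher power than Kruskal-Wallis at each correlation tried.

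Three practical objections are fair and are taken up in the fix: rhythm is listed among the vital signs but is categorical, three differences on three measures make nine intervals, and the document's past tense suggests that the data may already have been analysed.

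**Conclusion.** The point holds on either reading of the text. The test named for this outcome contains no arm contrast, the general test that may apply gives no estimate, and intervals are planned for vasodilation alone.

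The main loss is an interpretable between-arm result. The secondary loss is precision: the variance of an arm difference can be cut by 10% to 25% for ρ between 0.8 and 0.5, assuming equal pre and post SDs. These are illustrations, because the documents give no SD, expected change or correlation.

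Leaving out the initial value does not bias a randomised comparison. Adjusting for it does not remove the difference in waiting time ("The transdermal delivery method required an application time of at least 45 minutes, while lingual and sublingual nitroglycerin required 5 minutes application time"), which is part of the strategies being compared. As this is a secondary outcome and the remedy is nearly free, the change should be made, but the trial's primary result does not depend on it.

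**What to change.** For systolic pressure, diastolic pressure and heart rate, fit ANCOVA with the post-scan value as response, and randomised arm and initial value as predictors. Report the three pairwise arm differences with 95% confidence intervals. Say whether these nine intervals are unadjusted and descriptive, or use the 0.05/3 level that the sample-size paragraph sets for its three-group comparison. Keep the paired t-tests as description within arms, and say that they are by arm. State whether the Kruskal-Wallis sentence covers vital-sign changes. Summarise rhythm separately as a categorical variable.

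The cost is a few lines in Statistical Analysis and a short model fit; both readings are already collected. If the results have already been analysed, add the ANCOVA as a supplementary analysis labelled post hoc.
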